The **intensity of all adverse events**, including clinically significant treatment-emergent laboratory abnormalities, and potential systemic reactions, will be graded according to the National Cancer Institute **Common Terminology Criteria for Adverse Events** (CTCAE) Version 5.0. The CTCAE grade refers to the severity of the adverse event and ranges from Grade 1 (mild), Grade 2 (moderate), Grade 3 (severe) and Grade 4 (life-threatening or disabling) to Grade 5 (death related to adverse event).

Adverse events not listed in the CTCAE (e.g., physical signs or symptoms) will be classified as follows:

- **Mild:** discomfort noticed; no disruption of normal daily activity; no major impact on patient
- **Moderate:** discomfort sufficient to reduce or affect daily activity; causes minor inconvenience
- **Severe:** inability to work or perform normal daily activity; causes a substantial disruption to the patient's wellbeing
- **Life threatening:** represents an immediate threat to life

Relationship of Adverse Events to Study Procedure

	The PI will determine the relationship of AEs to the test procedure/device/agent as definitely related, probably related, possibly related, unrelated, or unknown.
	
The PI will use an alternative attribution scale (specify):
 
 • None: No relationship between the event and the study procedure. The event is related to other etiologies, such as concomitant medications or subject's clinical state. • Unlikely: The current state of knowledge indicates that a relationship to study procedure is unlikely or the temporal relationship would not have had any reasonable association with the observed event. • Possible: A reaction that follows a plausible temporal sequence from the study procedure and follows a known response pattern to the procedure. The reaction might have been produced by the subject's clinical state or other modes of therapy administered to the subject. • Probable: A reaction that follows a plausible temporal sequence from the study procedure and follows a known response pattern to the procedure and cannot be reasonably explained by the known characteristics of the subject's clinical state or other modes of therapy administered to the subject.

For the purpose of safety analyses, all adverse events that are classified as possible or probable will be considered treatment-related events.

REFERENCES

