Secondary aims of this study are:

- #1: To describe the effect of rimegepant on rectal compliance in participants with non-constipation IBS and chronic abdominal pain.
- #2: To evaluate the effects of rimegepant on rectal sensation based on ascending method of limits and on graded rapid phasic distensions in participants with non-constipation IBS and chronic abdominal pain.
- #3: To evaluate effects of rimegepant on overall colonic transit in participants with non-constipation IBS and chronic abdominal pain.
- #4: To evaluate safety of rimegepant in participants with non-constipation IBS and chronic abdominal pain.

METHODS

STUDY INTERVENTION AND CONCOMITANT THERAPY

Rimegepant

Rimegepant (Nurtec ODT®) is an oral, small molecule, CGRP receptor antagonist approved in the US for the acute treatment of migraine and the preventive treatment of episodic migraine in adults. This is a summary of the pharmacology and dosing of rimegepant in the proposed study:

- Approved Formulation – oral dissolving tablet (ODT)
- Dosing as per Migraine Prevention: 75 mg Every Other Day (EOD) for 4 weeks/28-32 days
- Pharmacokinetics: Tmax: 1.5h; $t_{1/2}$: 11h; bioavailability: 64%
- Drug-drug Interactions: Avoid strong CYP3A4 inducers and strong or moderate CYP3A4 inhibitors
- Hepatic and Renal Impairment: Avoid use in severe hepatic impairment and end stage renal disease
- Notable Adverse Events: nausea (2.7% in rimegepant group vs 0.8% in placebo group); abdominal pain/dyspepsia (2.4% in rimegepant group vs 0.8% in placebo group)

Description of Study Drug

Rimegepant is supplied as a 75 mg white to off-white ODT in a pre-filled blister card containing 8 tablets. The placebo is supplied as a 75 mg white to off-white ODT in a pre-filled blister card containing 8 tablets. Blister cards are to be stored at 15-25°C (59-77°F).

Blinding

Participants will be blinded to their assigned study intervention. Investigators and other site staff will be blinded to participants' assigned study intervention. Participants will be assigned to receive study intervention according to the assigned treatment group from the randomization scheme. Investigators will remain blinded to each participant's assigned study intervention throughout the course of the study.

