In order to maintain this blinding, the pharmacy at Mayo Clinic will be responsible for the preparation and dispensing of all study intervention and will endeavor to ensure that there are no differences in time taken to dispense or in visual presentation, following randomization or dispensing. The pharmacy will instruct the participant to avoid discussing the taste, dosing frequency, or packaging of the study intervention with the investigator.

Study Drug Administration

Rimegepant and the placebo are for oral administration only. Participants will administer 1 ODT every other day (EOD) for 4 weeks (28-32 days). Participant will administer the study

intervention by placing 1 ODT on or under the tongue and allowing to dissolve. Dosing should occur around the same time for each scheduled EOD dose. If a dose of study drug is missed, lost, or otherwise unable to be taken, the participant should note the missed dose and should not take another dose until the next scheduled dosing day.

Dose Modifications

Dose adjustment is not permitted. Dose interruption may be permitted for an adverse effect which is not so severe as to warrant medication discontinuation.

Concomitant Medications

Concomitant medications aimed at relief of visceral pain such as central neuromodulators will only be permitted if the dose has been constant for at least 30 days prior to randomization, and the dose will remain constant throughout the study and 4 week washout period. Strong CYP3A4 inhibitors and strong or moderate CYP3A4 inducers are prohibited while on study treatment (See Appendix 3).

[figure not shown]
RESCUE Medications: Any additional pain medications other than the medication to which a participant is randomized will need to be justified by the severity of the symptoms and with the approval of the senior clinical investigators (Dr [name] or Dr [name]).

Contraception

The investigator or their designee, in consultation with the participant, will confirm that the participant is utilizing an effective method of contraception for the individual participant and their partner(s) from the permitted list of contraception methods (see Appendix 4) and will confirm that the participant has been instructed in its consistent and correct use. Participants need to affirm their consistent and correct use of at least 1 of the selected methods of contraception, considering that their risk for pregnancy may have changed since the last visit.

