Run-in period: Two weeks prior to randomization a daily diary including pain will be provided for assessment of pain intensity. Abdominal pain intensity will be assessed by using a daily abdominal pain score by VAS that asks participants daily to rate their average abdominal pain over the past 24 hours. A score of ≥ 30 on the 100 mm VAS averaged over 7 consecutive days of the 2 week run-in period will be meaningful and adequate for randomization. In addition, stool form, frequency and ease of passage will be collected using the daily stool diary questionnaire. Bloating, flatulence, urgency, and most intense pain will also be collected.

Inclusion criteria:

1. Participants will be 18-70 years of age;
2. Participants will have non-constipation IBS [that is IBS-D (diarrhea), IBS-M (mixed), or IBS-U (unspecified)] with chronic abdominal pain diagnosed or documented in their medical records at Mayo Clinic with chronic pain documented for ≥ 3 months;
3. Participants will have subjective pain ratings of ≥ 30 on the 100 mm VAS during at least 7 consecutive days of the 2 week run-in period for enrollment; criterion required by FDA for recruitment of patients in therapeutic trials in IBS-pain;
4. Participants will be capable of providing informed consent.

Exclusion criteria:

1. Diagnosis of moderate-severe depression as per HADS ≥ 15 ;
2. Alcohol or illicit substance dependence or abuse in the past 12 months;
3. Dementia, unprovoked seizure history, seizure disorder;
4. Pregnancy (all women of childbearing potential will be required to have a negative pregnancy test prior to initiation, and will be on a highly effective method of contraception, as detailed in the consent form);
5. Significant change or increase in antidepressant or pain medications within the last four weeks; significant change in primary treatment interventions for pain in the past four weeks;
6. Medically unstable;
7. Severe hepatic or renal impairment, such as baseline AST or ALT >2.5 X upper normal limit or end-stage renal disease with estimated glomerular filtration rate or creatinine clearance <15 mL/min. Although Rimegepant is rarely associated with abnormal circulating liver enzymes, we shall exclude patients with baseline AST or ALT greater than 2.5 times the upper limit of normal;
8. Concomitant use of strong CYP3A4 inhibitors and strong or moderate CYP3A4 inducers;

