9. Participants who report nausea several times per week or daily on the baseline bowel disease questionnaire (question # 16) will be excluded from the study because of the low risk of nausea induced by the treatment which was estimated at approximately 3% for rimegepant compared to 1% for placebo.

Questionnaires, Clinical Evaluation and Data Collection

Questionnaire based data will be collected using validated questionnaires: (see appendix)

- Abridged Talley Bowel Disease Questionnaire⁴² for screening
- Talley Bowel Disease Questionnaire⁴²
- IBS Quality of Life Questionnaire⁴⁵
- Hospital Anxiety Depression Questionnaire⁴⁶
- Daily Likert Scale Questionnaire for Most Intense Pain (0-4)⁴³
- Daily Abdominal Pain Score by Visual Analog Pain Scale (VAS)
- Daily Abdominal Bloating Score by Visual Analog Pain Scale (VAS)
- Daily Abdominal Flatulence Score by Visual Analog Pain Scale (VAS)
- Daily Abdominal Urgency Score by Visual Analog Pain Scale (VAS)
- Daily Bowel Diary including Bristol Stool Form Scale⁴⁴

Participants must meet the inclusion and exclusion criteria previously described, and they will be evaluated by a study co-investigator prior to enrollment. Potential participants will then be invited for the screening examination.

Discontinuation of Study Intervention and Participant Withdrawal from Study

It may be necessary for a participant to permanently discontinue study intervention. Reasons for permanent discontinuation of study intervention include the following:

- Clinically significant safety reasons as judged by the investigator;
- Severe non-compliance to the protocol as judged by the investigator;
- Pregnancy;
- Development of a condition or acute event that necessitates treatment with one or more prohibited medications;
- Withdrawal of informed consent.

METHODS FOR PHYSIOLOGICAL ENDPOINTS

The standard scintigraphic method to measure colonic transit established in the Clinical Research Trials Unit (CRTU) at Mayo Clinic Rochester will be used to evaluate changes in colonic transit.⁴⁷⁻⁵⁰

Colonic transit

[figure not shown]
A validated scintigraphic method to measure gastric, small bowel, and colonic transit is shown.

Figure: Scintigraphic method to measure whole gut transit.

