APPENDIX 3 Prohibited Concomitant Medication

The following medications and medication combinations are strong inhibitors of CYP3A4. This list should not be considered all-inclusive. As described in the study protocol, concomitant use of strong CYP3A4 inhibitors is prohibited. Individual drug labels should be reviewed for specific information on propensity to cause strong inhibition of the CYP3A4 enzyme for a specific compound.

Strong CYP3A4 inhibitors
Boceprevir, cobicistat, conivaptan, danoprevir and ritonavir, elvitegravir and ritonavir, indinavir and ritonavir, itraconazole, ketoconazole, lopinavir and ritonavir, paritaprevir and ritonavir and (ombitasvir and/or dasabuvir), posaconazole, ritonavir, saquinavir and ritonavir, telaprevir, tipranavir and ritonavir, troleandomycin, voriconazole, clarithromycin, nefazodone, nelfinavir, mifepristone, mibefradil, telithromycin, troleandomycin

The following medications and supplements are moderate to strong inducers of CYP3A4. As described in the study protocol, concomitant use of moderate to strong CYP3A4 inducers is prohibited. This list should not be considered all-inclusive. Individual product labels should be reviewed for specific information on propensity to cause moderate to strong induction of the CYP3A4 enzyme for a specific compound.

Strong CYP3A4 inducers
Apalutamide, avasimibe, carbamazepine, phenytoin, rifampin, rifapentine, St. John's Wort

Moderate CYP3A4 inducers
Bosentan, efavirenz, etravirine, lopinavir, modafinil, nafcillin, rifabutin, phenobarbital

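### The drug summary and the operative medication rules attach the moderate CYP3A4 restriction to opposite classes, so moderate inhibitors are flagged but never excluded or listed

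*Combined protocol and SAP*

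**What the plan says.** Four places in the combined protocol and SAP state a CYP3A4 restriction.

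- **Study Intervention and Concomitant Therapy, Rimegepant.** The bulleted summary of the drug as used in this study has a drug-interaction line: "Avoid strong CYP3A4 inducers and strong or moderate CYP3A4 inhibitors".
- **Concomitant Medications**, in the same part of the protocol: "Strong CYP3A4 inhibitors and strong or moderate CYP3A4 inducers are prohibited while on study treatment". It refers the reader to Appendix 3.
- **Exclusion criteria, item 8:** "Concomitant use of strong CYP3A4 inhibitors and strong or moderate CYP3A4 inducers".
- **Appendix 3.** On inhibitors: "concomitant use of strong CYP3A4 inhibitors is prohibited". On inducers: "concomitant use of moderate to strong CYP3A4 inducers is prohibited". It has separate lists for strong inhibitors, strong inducers and moderate inducers. It has no list of moderate inhibitors.

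A fifth passage depends on these. The section on discontinuation gives as one reason for stopping study drug: "Development of a condition or acute event that necessitates treatment with one or more prohibited medications".

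**The concern.** In the drug summary the word moderate belongs to the inhibitors. In the three operative rules it belongs to the inducers. Eligibility will be decided from the exclusion list and Appendix 3, so a participant on a moderate inhibitor passes criterion 8 even though the summary says to avoid that class. In the other direction, a candidate on a moderate inducer is turned away under a restriction that the summary does not mention.

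Inhibitors and inducers of a metabolising enzyme bear on drug exposure, and for that reason the summary treats them as an interaction. The Dose Modifications paragraph permits no dose adjustment, so an affected participant would stay on the fixed dose. Safety is secondary aim 4 and a listed secondary endpoint. The summary also names abdominal pain/dyspepsia among the notable adverse events of rimegepant, and abdominal pain is the primary endpoint. Altered exposure in a participant on active drug could therefore reach both the safety and the efficacy readout.

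**Working it through.** The plan has no figure to reproduce here. The check compares the four statements class by class and then asks whether any other text closes the gap.

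| Class | Rimegepant summary | Concomitant Medications | Exclusion criterion 8 | Appendix 3 | Result |
|---|---|---|---|---|---|
| Strong inhibitors | avoid | prohibited | excluded | prohibited, listed | consistent |
| Strong inducers | avoid | prohibited | excluded | prohibited, listed | consistent |
| Moderate inhibitors | avoid | not named | not named | not named, no list | contradiction |
| Moderate inducers | not named | prohibited | excluded | prohibited, listed | contradiction, opposite direction |

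**Does other text resolve it?**

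1. *The open-ended list in Appendix 3.* The inhibitor list is introduced as follows: "The following medications and medication combinations are strong inhibitors of CYP3A4. This list should not be considered all-inclusive". The caveat extends a list of strong inhibitors to other strong inhibitors. The appendix's instruction to consult product labels is likewise limited to strong inhibition and to moderate or strong induction. Neither reaches moderate inhibitors.
2. *The discontinuation rule.* It is triggered by prohibited medications. Moderate inhibitors are not prohibited anywhere, so starting one during treatment does not trigger it.
3. *Status of the summary.* It is not remote background. It sits under the study-intervention heading, describes the drug as used in this trial, and is worded as a direction. The neighbouring line on hepatic and renal impairment uses the same verb, and exclusion criterion 7 deals with both impairments. The CYP3A4 line also has its exclusion criterion, but with the moderate class changed.
4. *Missing figure.* A figure not reproduced in the text follows the Concomitant Medications paragraph, and its content is unknown. The wording of that paragraph, criterion 8 and Appendix 3 is complete and mutually consistent without it.

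**Scale.** The Sample Size section gives n = 12 per treatment group.

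- Share of an arm for one participant: 1/12 = 0.083, or 8.3%.
- One additional participant with an adverse event in the active arm moves that arm's rate by 1/12 = 8.3 percentage points.
- A shift of *d* mm in one participant's average pain score moves the arm mean by *d*/12 mm.

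These figures hold for any participant in a trial of this size. They show how little averaging there is to absorb one affected participant, and they do not measure the interaction itself. They apply only to someone allocated to rimegepant, because a participant on placebo has no rimegepant exposure to alter.

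**The case against.** The strongest reply is that three operative texts agree and the outlier is one bullet in a summary. On that reading the bullet is a slip of transposition, the rule that staff apply is clear, and nobody is wrongly admitted. The documents allow this reading. They equally allow the reverse, and they give no reason for leaving moderate inhibitors out of the operative rules. Agreement among three places therefore does not settle which version is meant. What stands is that the defect runs both ways, and that harm from admitting users of moderate inhibitors follows only if the summary states the intended restriction.

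A second reply is that the clinical consequence is not shown. That is correct as to size: the documents contain no exposure figure for either moderate class. Nor do they give the chance that a participant takes a moderate inhibitor, is allocated to active drug and then has an event because of it. The 8.3% is generic.

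A third reply points to other safeguards. Concomitant medication is reviewed from screening to the end of treatment, a co-investigator evaluates each candidate before enrolment, and study drug can be stopped for clinically significant safety reasons. These make affected participants identifiable afterwards. None of them names moderate inhibitors, so none works as a screening rule for that class.

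**Conclusion.** The concern holds, and the text is wrong as written. The protocol contradicts itself on two of the four CYP3A4 classes, and nothing elsewhere reconciles it. A participant taking a class that the protocol says to avoid can meet every criterion on CYP3A4 medication and be randomised.

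Confidence in the contradiction is high, because it rests only on the wording. The size of the consequence cannot be derived from the documents. The number of affected participants may be zero, and any effect requires allocation to rimegepant. If there is one such participant, that person is 8.3% of an arm of 12. The point concerns eligibility and exposure. It changes no sample size, power or significance figure.

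**What to change.** The sponsor and investigators should decide which classes are restricted and then name the same inhibitor and inducer classes in all four places: the rimegepant summary, Concomitant Medications, exclusion criterion 8 and Appendix 3. This review takes no position on which version is right. The Appendix 3 lists should cover every class that is finally prohibited. The discontinuation rule needs no separate edit, because it refers to whatever is prohibited.

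Anyone already enrolled should be re-checked against the reconciled rule. The data for this should exist: the Schedule of Assessments records prior and concomitant medication at screening, run-in, baseline, treatment and end of treatment, and the daily diary asks about non-routine medicines.

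The cost is an amendment to protocol and appendix wording, a short review of medication records, and possibly a marginally smaller eligible pool. No endpoint or analysis changes.

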Figure shows experimental procedure for measurement of rectal compliance by ascending method of limits (AML), sensation thresholds (indicated by arrows) and sensation ratings by random order pressure distensions and recording symptoms using 100mm visual analog scales

Ascending method of limits: compliance and sensory thresholds

Rectal sensory thresholds and compliance are measured by ramp inflation, increasing in steps of 4 mm Hg for 1 minute per step from 0 to a maximum 60 mm Hg. Thresholds for gas, first desire to defecate, urgency, and pain are indicated by the study participants by pressing a button at the distension pressure at which sensations are perceived. Ramp inflation is

terminated as soon as participants reported the first sensation of pain.

The bag is deflated and BOP is determined by pressure in the bag increased from 4 mm Hg in steps of 2 mm Hg for 1 minute per step until respiratory excursions are observed. The baseline operating pressure (BOP) set 2 mm Hg above the minimal distension pressure at which respiratory excursions are clearly recorded from the barostat tracing. Once BOP is determined there is another rest for 10 minutes.

Random order phasic distensions: sensory ratings

Phasic distensions of 12, 24, 30 and 36 mm Hg above BOP are each applied once in random order, (the order being provided before the start of the study by the biostatistician), with the participants blinded to the distension order. Each distention is maintained for 60 seconds with an interval between distensions of 2 minutes with the balloon deflated to BOP. Distension pressure is associated with intensity ratings that are generally proportional to the magnitude of the distension pressures.⁵²⁻⁵⁴ Participants mark three separate 100 mm visual analog scales (VAS) 30 seconds after the onset of the distension for the sensations of gas, urgency, and pain. These scales are anchored at each end by the descriptions 'unnoticeable' and 'unbearable'. Pressure is immediately released if the participant reported greater than 80 mm of pain on the VAS scale and higher distensions are not subsequently administered. During the assessment of sensation, the interaction between the participant and the study investigator is kept to a

minimum. Participants will also complete another VAS questionnaire to describe their sense of tiredness, peace, worry and activity before the first measurement of sensation.

Data analysis for compliance and sensory endpoints

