The following measurements are derived: (i) the sensory thresholds for gas, first desire to defecate, urgency, and pain during ascending method of limits, (ii) the sensation score (gas, urgency, and pain) in response to the four phasic distensions (12, 24, 30 and 36 mmHg above BOP), and (iii) rectal compliance.

The sequential proportionate volumes (observed volume/maximum observed volume) will be used to obtain a pressure corresponding to half the maximum observed volume using a computer-based linear interpolation algorithm.⁵⁵ Thus, the summary value for each compliance curve will be calculated from the pressures corresponding to the volumes just above and just below the half maximum volume. This provides the specific pressure ($Pr\ 1/2$) corresponding to one half of the maximum observed volume, for each participant, where a smaller $Pr\ 1/2$ corresponds to higher rectal compliance.

STATISTICAL ANALYSIS

A. *Clinical Data*

- a. **Abdominal pain score:** the average pain score each day, as measured by the 100 mm VAS, over the treatment period will be calculated and compared between groups using an unpaired analysis (t test or rank sum test if not normally distributed). The averages during run-in 2-week period will be available to conduct analysis using the baseline measurement as covariates.
- b. **Clinical scales for depression, quality of life** (HADS and IBS-QOL). These summaries will be obtained from measurements made at baseline, at the end of treatment, and 4 weeks after treatment ends.

In addition to calculating these summaries, demographic and other information, including participant age and gender, as well as other medications will be recorded for each participant and summarized as appropriate for the type of data.

Treatment success for chronic pain is defined as a 30% decline in subjective pain ratings on visual analog scales for the treatment group compared to the placebo treatment group. An “Intent to Treat” data analysis will be used given the possibility that some participants will not be able to complete the study. Descriptive statistical analysis and unpaired t-tests (or rank sum test) will be used.

B. *Physiological Data*

Colonic Transit

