A “time to event” approach (i.e. pressure required to evoke specific sensations) will be used to assess four sensation thresholds (first desire to defecate, gas, urgency, and pain). Since some threshold levels are “censored” (e.g. pain not evoked by the maximum distension pressure used according to the protocol approved by the IRB), a Kaplan-Meier summary of the pressure thresholds will be used to univariately depict the cumulative probability of evoking the sensation, and proportional hazards regression models will be used to assess group effects separately for each of the sensation types. The same covariates listed above used in the analyses of sensation VAS ratings will be included in the proportional hazards regression models, in particular the ratings of “tiredness”, “peace”, “worried”, and “activity” recorded during the sensation studies.

Rectal compliance

The covariates included in the ANCOVA models for fasting colonic tone and compliance $Pr \frac{1}{2}$ values will be age, gender, BMI, the “tiredness”, “peace”, “worried”, and “activity” scores, the HAD scores, and the BDQ somatic symptom score.

Endpoints

Primary Endpoint

is abdominal pain scores in participants with non-constipation IBS

Summary of Secondary Endpoints will be focused on characterizing rectal compliance and sensation, and colonic transit,

The *secondary endpoints* for analysis will be:

- a. Colonic transit geometric center at 24 hours
- b. Colonic transit geometric center at 48 hours
- c. Gastric emptying of solids $T_{1/2}$ (minutes) and % emptied at 4h
- d. Rectal compliance
- e. Rectal sensation during ascending method of limits
- f. Rectal sensation during random order, graded phasic distensions
- g. IBS-QOL
- h. Safety/adverse effects

Sample Size

This study is meant to be a pilot study that will provide preliminary information regarding the usefulness of treating participants chronic abdominal pain associated with non-constipation IBS with rimegepant.

The estimated effect size (with $n=12$ per treatment group) for each of the primary and secondary endpoints is based on power calculation using data acquired from patients with IBS-D at Mayo Clinic^{56, 57}.

Table 4. Key Gastrointestinal Physiologic Data in 163 People Based on Bowel Function Subgroup

	Healthy controls	IBS-C	IBS-D	IBS-M
Number of males	41 (0)	49 (0)	44 (3)	29 (0)
Fasting gastric volume, mL	226 ± 11	229 ± 11	247 ± 11	222 ± 12
Postprandial gastric volume, mL	736 ± 13	740 ± 14	735 ± 14	770 ± 17

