Radiation exposure in this study involves radiation exposure from the ¹¹¹In used to measure colonic transit. These exposures conform to previously approved levels of radiation exposure approved by the Radiation Control Committee at Mayo Clinic. The radiation dosimetry and organ exposures (in mrad) are listed below.

GASTROINTESTINAL AND COLONIC TRANSIT TESTS

Radiopharmaceutical	Act mCi	Body	Gonads	Breast	Red marrow	Lung	Thyroid	Bone	ULI	Colon	Stom	Blad	Liv	Esoph	Other
											-ach	-der	-er	-agus	
¹¹¹ In charcoal	0.10	20	140		20				380	740	60	40	10	160	
^{99m} Tc-sulfur colloid	1.0	20	90		20				420	300	130	20	10	220	

(mrad= unit of radiation absorbed dose to organs)

H_e or the radiation effective dose to the body summarizes the risk to the whole body as the individual doses to each of the organs; effective dose is used to compare risks among various types of x ray and radionuclide studies: ¹¹¹In Cl₃ 0.1 mCi : H_e 142 mrem (where mrem= radiation equivalent dose); ^{99m}Tc sulfur colloid 1.0 mCi, H_e = 90 mrem; note that participants will receive ¹¹¹In on 2 occasions separated by about 1 month

In view of the radiation exposure, all females of childbearing age will be required to have a negative urine pregnancy test within 48 hours of performance of fluoroscopy or the radioisotope studies.

Significance of the Proposal

Rimegepant, at doses and mode of administration approved by FDA for the prophylaxis of migraine headache, will be efficacious in the reduction of abdominal pain and rectal sensation in participants with non-constipation IBS and abdominal pain.

This study will provide preliminary data to support the calculation of the variance in response and therefore plan a future controlled trial.

Gender/Minority Mix

All efforts will be made to recruit participants of both genders, and of diverse ethnicity.

HUMAN STUDIES PROTECTION

I. CONFIDENTIALITY

Mayo Clinic upholds the most stringent standards for protection of human subjects and privacy while balancing the crucial importance of data sharing to advance medical science. This is applied to all patients participating in research activities, direct care and as study participants. Protection of privacy is assured based on Mayo Clinic's standards and procedures, including rules in full compliance with current HIPAA regulations. All staff members are trained in privacy compliance and held to the strictest standards.

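### Pr1/2 is scaled to the largest volume reached before pain stops the ramp, so a treatment that only raises the pain threshold can look like lower rectal compliance

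*Combined protocol and SAP*

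**What the plan says.** One ramp serves two purposes. The section on the ascending method of limits states: "Rectal sensory thresholds and compliance are measured by ramp inflation, increasing in steps of 4 mm Hg for 1 minute per step from 0", with a ceiling of 60 mm Hg. The ramp is "terminated as soon as participants reported the first sensation of pain". The statistical section on sensation pressure thresholds allows for thresholds that are never reached ("pain not evoked by the maximum distension pressure used according to the protocol approved by the IRB"); in those participants the ceiling ends the ramp.

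The section on data analysis for compliance and sensory endpoints then defines the summary: "The sequential proportionate volumes (observed volume/maximum observed volume) will be used to obtain a pressure corresponding to half the maximum observed volume". Pr1/2 is thus each participant's own pressure "corresponding to one half of the maximum observed volume". The section gives the direction of reading: "where a smaller $Pr\ 1/2$ corresponds to higher rectal compliance".

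The ANCOVA for compliance (Statistical Analysis, Rectal compliance) lists age, gender, BMI, the four mood and arousal scores, the HAD scores and the somatic symptom score. It lists neither the pressure or volume at which the ramp ended nor baseline Pr1/2. No common pressure range is set. The Schedule of Assessments places the barostat study at baseline and at end of treatment, so two curves per participant are planned.

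Under Significance of the Proposal, the expectation is that rimegepant "will be efficacious in the reduction of abdominal pain and rectal sensation in participants with non-constipation IBS and abdominal pain". Compliance is secondary aim 1 and sensation is secondary aim 2.

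**The concern.** The reference volume in Pr1/2 is not a property of the rectum alone. It is the volume reached when the participant first reports pain, and the drug is expected to change that report. If pain comes later on active treatment, the ramp ends at a higher pressure and usually a larger volume. Half of that volume is then reached at a higher pressure, and Pr1/2 rises.

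Randomisation does not protect against this, because the difference in ramp length would itself be a treatment effect. An analgesic effect could be reported as a stiffer rectum, or could cancel a real gain in compliance. The study is meant to inform a later controlled trial, so either misreading would carry forward.

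**Working it through.** **Inputs.** From the effect-size table under Sample Size: Pr1/2 mean 14.2, SD 3.94, detectable difference 4.7 mm Hg; pain threshold mean 31, SD 11.81, detectable difference 13.3 mm Hg; 12 per arm, 80% power, alpha 0.05. From the barostat method: 4 mm Hg steps, 60 mm Hg ceiling. Curve shape is an assumption, because the documents report no rectal volumes.

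**The plan's own figure.** For a two-sided two-sample t test with 12 per arm and 80% power, the detectable standardised difference is 1.197. Then 1.197 × 3.94 = 4.72 mm Hg, which agrees with the stated 4.7. (For pain threshold the same method gives 1.197 × 11.81 = 14.1, not 13.3. The table's 13.3 is used below only as a scenario.)

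**Direction.** Let V(P) be the volume at pressure P and T the pressure at which the ramp ends. Pr1/2 solves V(Pr1/2) = V(T)/2. If V does not fall as pressure rises, V(T)/2 cannot fall as T rises, and neither can Pr1/2. The artefact therefore points to lower apparent compliance whatever the shape.

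**Size.** Take V(P) = 1 − exp(−(P/k)^b). Then Pr1/2 = k × [−ln(1 − V(T)/2)]^(1/b). For each b, choose k so that Pr1/2 = 14.2 at T = 31, then raise T and leave the curve unchanged.

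Example, b = 1, k = 91.97:
- T = 31: V = 0.286, Pr1/2 = 91.97 × −ln(1 − 0.1431) = 14.2.
- T = 31 + 13.3 = 44.3: V = 0.382, Pr1/2 = 91.97 × −ln(1 − 0.1911) = 19.5, a shift of +5.3.

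| b | Share of limiting volume at 31 mm Hg | Shift, T = 35 (+4) | Shift, T = 44.3 (+13.3) | Last shift as % of 4.7 |
|---|---|---|---|---|
| 1 | 29% | +1.65 | +5.3 | 113% |
| 1.5 | 82% | +0.81 | +2.0 | 43% |
| 2 | 96% | +0.27 | +0.46 | 10% |
| 2.2 | 98% | +0.15 | +0.22 | 5% |

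Other shapes widen the range a little. A straight line has Pr1/2 = T/2, so the shifts are 4/2 = +2.0 and 13.3/2 = +6.65, although it gives 15.5 rather than 14.2 at T = 31. A steep logistic curve that is flat by 31 mm Hg gives 0.

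**Does the planning ratio choose among shapes?** 14.2/31 = 0.46. Every calibrated curve in the table reproduces this value by construction, so it does not.

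**Checking the remedy.** Assume an unchanged wall, thresholds with SD 11.81, a 13.3 mm Hg drug effect, 4 mm Hg steps, the 60 mm Hg ceiling, and a baseline-to-end correlation in threshold of 0.5 to 0.7 (assumed).
- End-of-treatment Pr1/2 as now defined differs spuriously between arms by +5.0 mm Hg (b = 1) or +0.8 (b = 2.2).
- If both curves are cut at the participant's lower terminating pressure but only end-of-treatment values are compared, +1.4 to +1.6 (b = 1) or +0.4 to +0.5 (b = 2.2) remains. With b = 1 and correlation 0.9, about +0.8 remains. The reason is that the mean cut-off still differs by arm, at about 32 to 33 mm Hg on active and 28 to 30 on placebo for correlations of 0.5 to 0.7.
- If the within-participant change on the common range is compared, an unchanged curve gives the same Pr1/2 at both visits, so the spurious difference is exactly 0.

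**The case against.** The strongest reply is that the size is assumed. With no volumes in the documents, the range runs from negligible to more than the whole detectable difference. If rectal volume has nearly levelled off by the pain threshold, the artefact is trivial. The upper end needs a curve at only 29% of its limiting volume when pain is felt, and nothing in the documents supports that in particular. The 13.3 mm Hg scenario is a detectable difference, 43% of the mean, and not an expected effect. All of this stands, and it is why the 4 mm Hg figures are shown beside it.

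A reader might infer that 14.2/31 = 0.46, being close to the 0.50 of a straight line, makes the large shifts likely. It does not, because the saturating curves give the same ratio.

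A reader might also infer that aims 1 and 2 cannot be told apart. That goes too far. Pr1/2 does not enter any sensory endpoint. The pain threshold has its own analysis with censoring, and aim 2 also uses phasic distensions at preset pressures above the baseline operating pressure. A rise in Pr1/2 accompanied by a raised pain threshold would be visible in the planned outputs.

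Aim 1 is descriptive, the study is a pilot, and the interpolation method cites a methods comparison. These points lower the weight, but none makes Pr1/2 independent of where the ramp stops.

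**Conclusion.** The concern holds as a possible one-way distortion of the compliance endpoint. The mechanism and its direction follow from the plan's own definitions together with a volume that does not fall as pressure rises. Nothing in the compliance model corrects for it.

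For the assumed calibrated curves the shift is +0.15 to +1.65 mm Hg for one 4 mm Hg step and +0.2 to +5.3 mm Hg for a 13.3 mm Hg rise, against 4.7 mm Hg detectable. The documents favour neither end. In participants who report no pain, the ceiling and not pain sets the maximum. The documents do not show that compliance results will be wrong, or that the sensory results are affected.

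**What to change.** Specify before unblinding:

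1. For each participant, cut the baseline and end-of-treatment curves at the lower of the two terminating pressures and recompute Pr1/2 at both visits on that common range.
2. Compare the within-participant change between arms. Do not compare the truncated end-of-treatment value alone, which leaves part of the artefact.
3. Report this beside Pr1/2 as now defined, and read any rise in the latter together with the pain-threshold result.
4. State that participants without a second ramp contribute only to the display of Pr1/2 as now defined.

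The on-treatment pain threshold should not be added as a covariate instead, because it is a post-randomisation outcome.

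The cost is programming on data the plan already collects; the ramp procedure and its stopping rule are untouched. The downsides are that some upper points go unused, the change score may be noisier, and the truncated value is not comparable with the historical 14.2 mm Hg. The 4.7 mm Hg detectable difference therefore does not carry over to it.
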